#### **11.33 Measurement at Follow-up Evaluation:**

A subsequent scan must be obtained a minimum of 4 weeks following initial documentation of an objective status of either complete response (irCR) or partial response (irPR).

In the case of stable disease (SD), follow-up measurements must have met the SD criteria at least once after study entry at a minimum interval of 6 weeks (see Section 11.44).

NOTE: Once patient has had SD for  $\geq 6$  months, scanning can be reduced to every 3 months.

The cytological confirmation of the neoplastic origin of any effusion that appears or worsens during treatment when the measurable tumor has met criteria for response or stable disease is mandatory to differentiate between response or stable disease (an effusion may be a side effect of the treatment) and progressive disease.

- Cytologic and histologic techniques can be used to differentiate between PR and CR in rare cases (e.g., residual lesions in tumor types such as germ cell tumors, where known residual benign tumors can remain.)

#### 11.4 Measurement of Effect

##### 11.4.1 Target Lesions & Target Lymph Nodes

- Measurable lesions (as defined in Section 11.21) up to a maximum of 5 lesions, representative of all involved organs, should be identified as “Target Lesions” and recorded and measured at baseline. These lesions can be non-nodal or nodal (as defined in 11.21), where no more than 2 lesions are from the same organ and no more than 2 malignant nodal lesions are selected.
- Note: If fewer than 5 target lesions and target lymph nodes are identified (as there often will be), there is no reason to perform additional studies beyond those specified in the protocol to discover new lesions.
- Target lesions and target lymph nodes should be selected on the basis of their size, be representative of all involved sites of disease, but in addition should be those that lend themselves to reproducible repeated measurements. It may be the case that, on occasion, the largest lesion (or malignant lymph node) does not lend itself to reproducible measurements in which circumstance the next largest lesion (or malignant lymph node) which can be measured reproducibly should be selected.
- Baseline Sum of Dimensions (BSD): A sum of the longest diameter for all target lesions plus the sum of the short axis of all the target lymph nodes will be calculated and reported as the baseline sum of dimensions (BSD). The BSD will be used as reference to further characterize any objective tumor response in the measurable dimension of the disease.
- Post-Baseline Sum of the Dimensions (PBSD, or irPBSD for irRECIST): A sum of the longest diameter for all target lesions plus the sum of the short axis of all the target lymph nodes (and for irRECIST, plus the sum of new measurable lesions) will be calculated and reported as the post-baseline sum of dimensions (PBSD, or irPBSD for irRECIST). If the radiologist is able to provide an actual measure for the target lesion (or target lymph node), that should be recorded, even if it is below 0.5 cm. If the target lesion (or target lymph node) is believed to be present and is faintly seen but too small to measure, a default value of 0.5 cm should be assigned. If it is the opinion of the radiologist that the target lesion or target lymph node has likely disappeared, the measurement should be recorded as 0 cm.
- The minimum sum of the dimensions (MSD, or irMSD for irRECIST) is the minimum of the BSD and the PBSD (or the irPBSD for irRECIST)

**11.42 Non-Target Lesions & Non-Target Lymph Nodes**

Non-measurable sites of disease (Section 11.22) are classified as non-target lesions or non-target lymph nodes and should also be recorded at baseline. These lesions and lymph nodes should be followed in accord with Section 11.443.

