#### 11.22 Non-Measurable Disease

11.221 All other lesions (or sites of disease) are considered non-measurable disease, including pathological nodes (those with a short axis  $\geq 1.0$  to  $<1.5$  cm). Bone lesions, leptomeningeal disease, ascites, pleural/ pericardial effusions, lymphangitis cutis/pulmonis, inflammatory breast disease, and abdominal masses (not followed by CT or MRI), are considered as non-measurable as well.

Note: 'Cystic lesions' thought to represent cystic metastases can be considered as measurable lesions, if they meet the definition of measurability described above. However, if non-cystic lesions are present in the same patient, these are preferred

for selection as target lesions. In addition, lymph nodes that have a short axis  $<1.0$  cm are considered non-pathological (i.e., normal) and should not be recorded or followed.

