**11.432 irRECIST Overall Tumor Assessments****11.4321 irRECIST Complete Response (irCR):**

- a. Complete disappearance of all measurable and non-measurable lesions, and
- b. Each target lymph node must have reduction in short axis to <1.0 cm.

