**11.44 RECIST 1.1 Response Criteria**

11.441 All target lesions and target lymph nodes followed by CT/MRI/PET-CT/Chest X-ray/physical examination must be measured on re-

evaluation at evaluation times specified in Section 11.1. Specifically, a change in objective status to either a PR or CR cannot be done without re-measuring target lesions and target lymph nodes.

**Note:** Non-target lesions and non-target lymph nodes should be evaluated at each assessment, especially in the case of first response or confirmation of response. In selected circumstances, certain non-target organs may be evaluated less frequently. For example, bone scans may need to be repeated only when complete response is identified in target disease or when progression in bone is suspected.

11.442 Evaluation of Target Lesions

Complete Response (CR): All of the following must be true:

- a. Disappearance of all target lesions.
- b. Each target lymph node must have reduction in short axis to  $<1.0$  cm.

Partial Response (PR): At least a 30% decrease in PBSD (sum of the longest diameter for all target lesions plus the sum of the short axis of all the target lymph nodes at current evaluation) taking as reference the BSD (see Section 11.41).

Progression (PD): At least one of the following must be true:

- c. At least one new malignant lesion, which also includes any lymph node that was normal at baseline ( $<1.0$  cm short axis) and increased to  $\geq1.0$  cm short axis during follow-up.
- d. At least a 20% increase in PBSD (sum of the longest diameter for all target lesions plus the sum of the short axis of all the target lymph nodes at current evaluation) taking as reference the MSD (Section 11.41). In addition, the PBSD must also demonstrate an absolute increase of at least 0.5 cm from the MSD.
- e. See Section 11.32 for details in regards to the requirements for PD via FDG-PET imaging.

Stable Disease (SD): Neither sufficient shrinkage to qualify for PR, nor sufficient increase to qualify for PD taking as reference the MSD.

11.443 Evaluation of Non-Target Lesions & Non-target Lymph Nodes

Complete Response (CR): All of the following must be true:

- a. Disappearance of all non-target lesions.
- b. Each non-target lymph node must have a reduction in short axis to  $<1.0$  cm.

Non-CR/Non-PD: Persistence of one or more non-target lesions or non-target lymph nodes.

Progression (PD): At least one of the following must be true:

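### Measurable lesions left unselected as targets fall into no lesion class, so their unequivocal growth cannot turn a RECIST partial response into progression in the phase II primary endpoint

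*Combined protocol and SAP*

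**What the plan says.** Section 11.41 (printed as 11.4.1) draws targets from measurable disease: "Measurable lesions (as defined in Section 11.21) up to a maximum of 5 lesions", with the further limit that "no more than 2 lesions are from the same organ and no more than 2 malignant nodal lesions are selected". It adds that if the largest lesion cannot be measured reproducibly, it is passed over, in "which circumstance the next largest lesion (or malignant lymph node) which can be measured reproducibly should be selected".

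Section 11.42 defines the non-target class: "Non-measurable sites of disease (Section 11.22) are classified as non-target lesions or non-target lymph nodes". Section 11.22 defines non-measurable disease by exclusion from Section 11.21: "All other lesions (or sites of disease) are considered non-measurable disease". Section 11.21 sets measurability by size and method of assessment, not by whether the lesion was chosen as a target.

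Under RECIST 1.1 (Sections 11.442 and 11.443), complete response requires "Disappearance of all target lesions" and "Disappearance of all non-target lesions", plus node criteria for each class. Progression in disease present at baseline comes either from the target sum or from unequivocal progression of non-target disease. A NOTE in 11.443 says that the latter should not ordinarily override target status and must reflect a change in the disease overall. Sections 11.45 and 11.451 combine target status, non-target status and new sites, and nothing else.

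The irRECIST complete response (11.4321) is worded more broadly: "Complete disappearance of all measurable and non-measurable lesions, and" a node criterion.

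Section 11.0 makes RECIST 1.1 the criterion for the primary endpoint. Section 16.112 makes that endpoint confirmed ORR, counting CR or PR, with a stop at 1 or fewer of 9 and a promising verdict at more than 5 of 23.

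**The concern.** A patient with four measurable liver metastases can have only two of them as targets. The other two are too large to be non-measurable, so Section 11.42 does not take them in, and they are not new. The plan requires nobody to record them at baseline or to assess them later. If the two targets shrink by 30% while the other two clearly enlarge, the status table sees only the shrinkage.

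What is at stake is the numerator of the primary endpoint, in a design where one response can decide whether the trial continues or whether the combination is called promising. RECIST PFS, duration of response and disease control rate (goal 2.23) rest on the same status table and can miss the same progression. The error in ORR runs in the favourable direction.

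**Working it through.** **Step 1. Classify an unselected measurable lesion.**

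| Class | Entry condition | Does the lesion enter? |
|---|---|---|
| Target (11.41) | Measurable and selected within the limits | No, not selected |
| Non-target (11.42) | Non-measurable under 11.22 | No, measurable under 11.21 |
| New disease (11.442, 11.443) | Absent, or a normal node, at baseline | No, present at baseline |

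Three routes lead here: exceeding a limit (five in total, two per organ, two nodes); being passed over as not reproducibly measurable (11.41); and a measurable cystic lesion passed over for a non-cystic one (note in 11.22).

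**Step 2. Run the status table (11.451) with no new sites.**

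| Targets | Recorded non-targets | Unselected measurable lesion | Status as written | Status if the lesion were non-target |
|---|---|---|---|---|
| PR | Non-CR/Non-PD | Unequivocal growth, representative of overall disease | PR (responder) | PD (not a responder) |
| PR | Non-CR/Non-PD | Growth not representative of overall disease | PR | PR (NOTE in 11.443) |
| CR | CR | Persists, not growing | CR | PR |

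Only the first row changes the ORR count. Because the endpoint is confirmed response, the growth must also be present by the confirming scan, at least 4 weeks later (11.33). Growth after that leaves ORR alone and affects duration of response and PFS. The third row changes the label but not the count, since CR and PR both count as response. The label still matters in two places: it disagrees with irCR on the same scan, and a confirmed RECIST 1.1 CR is one of the retreatment criteria (3.32 and 7.5).

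**Step 3. Reproduce the plan's design figures (16.112).** Let X1 ~ Bin(9, p) and X2 ~ Bin(14, p).

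- Early stopping at p = 0.15: P(X1 ≤ 1) = 0.5995 (plan: 60%).
- P(promising) = Σ over x = 2 to 9 of P(X1 = x) · P(X2 ≥ 6 − x).
- At p = 0.15 this is 0.0990 (plan: controlled at 10%). At p = 0.35 it is 0.8037 (plan: 80%).

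The design is correctly stated, and its type I error lies just under its limit.

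**Step 4. Scale of one false response, true ORR 15%.** Assume that exactly one false response occurs and falls where it counts.

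- Stage 1 boundary: P(X1 = 1) = 0.368. The false response turns 1 of 9 into 2 of 9, so accrual continues. A promising verdict then needs at least 4 of the next 14: P(X2 ≥ 4) = 0.147. Contribution: 0.368 × 0.147 = 0.054.
- Final boundary: P(X1 ≥ 2 and total = 5) = 0.092. The false response makes it 6 of 23.
- Probability that the final verdict is reversed: 0.054 + 0.092 = 0.146.

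This is conditional on the false response. It is not an error rate for the trial.

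**Step 5. Assumed range.** The documents give no misclassification rate. If a share m of true non-responders were counted as responders, a true ORR of 15% would be observed as 0.15 + 0.85m:

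| m (assumed) | Observed ORR | P(promising) |
|---|---|---|
| 0 | 15.0% | 9.9% |
| 1% | 15.85% | 12.1% |
| 2% | 16.7% | 14.6% |
| 3% | 17.55% | 17.2% |
| 5% | 19.25% | 23.2% |

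Nothing in the documents says where in this range, or outside it, the trial would fall.

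**The case against.** The best reply is that Section 11.42 says non-measurable sites are non-target and does not say that nothing else is. Section 11.0 names the RECIST 1.1 guideline, and a footnote to 11.451 says that the template was revised to match it. An experienced reader may therefore treat any unselected lesion as non-target. That may well happen in practice. It does not repair the text: Section 11.0 says that the specifics follow in the protocol, and those specifics supply a definition that leaves this category out. A reader who follows the page and one who fills the gap from elsewhere can score the same patient differently, and the analysis plan in Section 16.3 does not settle it.

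The reply is stronger on reach, and that part stands:

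- The NOTE in 11.443 means that growth in other lesions would not automatically override a target PR even after the fix.
- Targets are chosen on size and must represent all involved sites, so many unselected lesions will be smaller ones in organs already represented.
- New lesions still give PD.
- Symptomatic deterioration (11.46) can also give PD, but through weight loss or performance status rather than lesion growth.

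A reader might infer that persistence of unselected lesions also inflates ORR. It does not, because CR and PR both count. A reader might also infer that every patient with more than two measurable lesions in an organ is affected. The gap applies to such patients, but their ORR status changes only with discordant, representative growth.

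**Conclusion.** The gap is real on the text. Unselected measurable lesions have no class, need not be recorded or followed, and cannot make a patient PD under 11.443 and 11.451. A target PR with representative growth in such lesions is counted as a RECIST response, and RECIST PFS, duration of response and disease control can miss that progression. Persistence affects only the CR label, its agreement with irCR, and the confirmed-CR retreatment criterion.

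The size of the effect on ORR cannot be derived from the documents. The figure of about 0.15 is a measure of sensitivity: it assumes a true ORR of 15% and one false response placed where it matters. A reader might instead add the two boundary probabilities, 0.368 + 0.092 = 0.460, and call that the chance of a wrong decision. The design does not support this, because crossing the stage 1 boundary only continues accrual and the final verdict still needs at least four more responses. Nor does anything show that the sponsor intended the narrower definition; it reads as an omission.

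The definition should be corrected because it governs the primary endpoint and the repair is small. The sample size and decision rules are not in question.

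**What to change.** In Section 11.42, state that all lesions and pathological lymph nodes not selected as target, including measurable ones beyond the limits in Section 11.41 or passed over during selection, are classified as non-target, recorded at baseline and followed per Section 11.443.

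Sections 11.443 and 11.451 then work unchanged, including the NOTE on representative progression. RECIST CR would require these lesions to disappear, or nodes to fall below the 1.0 cm short axis, which removes this source of disagreement with irCR.

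The cost is one sentence and extra rows on the baseline lesion form. The lesions are on scans already taken, so no imaging is added. The type I error (0.0990), power (0.8037) and sample size do not change. The observed ORR may be slightly lower. If patients have already been enrolled, their baseline scans would need to be re-read so that all are scored by the same rule.

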**11.43 irRECIST Response Criteria**

11.431 All target lesions and target lymph nodes followed by CT/MRI/PET-CT/Chest X-ray/physical examination must be measured on re-evaluation at evaluation times specified in Section 11.1. Specifically, a change in objective status to either irPR or irCR cannot be done without re-measuring target lesions and target lymph nodes.

**Note:** Non-target lesions and non-target lymph nodes should be evaluated at each assessment, especially in the case of first response or confirmation of response. In selected circumstances, certain non-target organs may be evaluated less frequently. For example, bone scans may need to be repeated only when complete response is identified in target disease or when progression in bone is suspected.

**11.432 irRECIST Overall Tumor Assessments****11.4321 irRECIST Complete Response (irCR):**

- a. Complete disappearance of all measurable and non-measurable lesions, and
- b. Each target lymph node must have reduction in short axis to <1.0 cm.

**11.4322 irRECIST Partial Response (irPR):**

- a. At least a 30% decrease in irPBSD (sum of the longest diameter for all target lesions plus the sum of the short axis of all the target lymph nodes at current evaluation, plus the measurements of new measurable lesions) taking as reference the BSD (see Section 11.41), and
- b. Non-target lesions are irNN (no target disease was identified at baseline and at follow-up the patient fails to meet criteria for irCR and irPD), and
- c. No unequivocal progression of new non-measurable lesions.

**11.4323 irRECIST Stable Disease (irSD):**

- a. Failure to meet criteria for irCR or irPR in the absence of irPD.

**11.4324 irRECIST Progression (irPD):**

- a. At least a 20% increase in irPBSD taking as reference the irMSD (see Section 11.41) with an absolute increase of at least 0.5 cm from the irMSD, or
- b. Unequivocal irPD for non-target or new non-measurable lesions.

**11.44 RECIST 1.1 Response Criteria**

11.441 All target lesions and target lymph nodes followed by CT/MRI/PET-CT/Chest X-ray/physical examination must be measured on re-

evaluation at evaluation times specified in Section 11.1. Specifically, a change in objective status to either a PR or CR cannot be done without re-measuring target lesions and target lymph nodes.

**Note:** Non-target lesions and non-target lymph nodes should be evaluated at each assessment, especially in the case of first response or confirmation of response. In selected circumstances, certain non-target organs may be evaluated less frequently. For example, bone scans may need to be repeated only when complete response is identified in target disease or when progression in bone is suspected.

11.442 Evaluation of Target Lesions

Complete Response (CR): All of the following must be true:

- a. Disappearance of all target lesions.
- b. Each target lymph node must have reduction in short axis to  $<1.0$  cm.

Partial Response (PR): At least a 30% decrease in PBSD (sum of the longest diameter for all target lesions plus the sum of the short axis of all the target lymph nodes at current evaluation) taking as reference the BSD (see Section 11.41).

Progression (PD): At least one of the following must be true:

- c. At least one new malignant lesion, which also includes any lymph node that was normal at baseline ( $<1.0$  cm short axis) and increased to  $\geq1.0$  cm short axis during follow-up.
- d. At least a 20% increase in PBSD (sum of the longest diameter for all target lesions plus the sum of the short axis of all the target lymph nodes at current evaluation) taking as reference the MSD (Section 11.41). In addition, the PBSD must also demonstrate an absolute increase of at least 0.5 cm from the MSD.
- e. See Section 11.32 for details in regards to the requirements for PD via FDG-PET imaging.

Stable Disease (SD): Neither sufficient shrinkage to qualify for PR, nor sufficient increase to qualify for PD taking as reference the MSD.

11.443 Evaluation of Non-Target Lesions & Non-target Lymph Nodes

Complete Response (CR): All of the following must be true:

- a. Disappearance of all non-target lesions.
- b. Each non-target lymph node must have a reduction in short axis to  $<1.0$  cm.

Non-CR/Non-PD: Persistence of one or more non-target lesions or non-target lymph nodes.

Progression (PD): At least one of the following must be true:

- a. At least one new malignant lesion, which also includes any lymph node that was normal at baseline ( $<1.0$  cm short axis) and increased to  $\geq1.0$  cm short axis during follow-up.

- b. Unequivocal progression of existing non-target lesions and non-target lymph nodes. (NOTE: Unequivocal progression should not normally trump target lesion and target lymph node status. It must be representative of overall disease status change.)
- c. See Section 11.32 for details in regards to the requirements for PD via FDG-PET imaging.

#### 11.45 RECIST 1.1 Overall Objective Status

The overall objective status for an evaluation is determined by combining the patient's status on target lesions, target lymph nodes, non-target lesions, non-target lymph nodes, and new disease as defined in the following tables:

##### 11.451 For Patients with Measurable Disease

Target Lesions & Target Lymph Nodes	Non-Target Lesions & Non-Target Lymph Nodes	New Sites of Disease	RECIST 1.1 Overall Objective Status
CR	CR	No	CR
CR	Non-CR/Non-PD	No	PR
PR	CR Non-CR/Non-PD	No	PR
CR/PR	Not All Evaluated*	No	PR**
SD	CR Non-CR/Non-PD Not All Evaluated*	No	SD
Not all Evaluated	CR Non-CR/Non-PD Not All Evaluated*	No	Not Evaluated (NE)
PD	Uequivocal PD CR Non-CR/Non-PD Not All Evaluated*	Yes or No	PD
CR/PR/SD/PD/Not all Evaluated	Uequivocal PD	Yes or No	PD
CR/PR/SD/PD/Not all Evaluated	CR Non-CR/Non-PD Not All Evaluated*	Yes	PD

\*See Section 11.441

\*\* NOTE: This study uses the protocol RECIST v1.1 template dated 2/16/2011. For data collection and analysis purposes the objective status changed from SD to PR in the MCCC protocol RECIST v1.1 template as of 2/16/2011 and to match RECIST v1.1 requirements.

#### 11.46 Symptomatic Deterioration

Patients with global deterioration of health status requiring discontinuation of treatment without objective evidence of disease progression at that time, and not either related to study treatment or other medical conditions, should be reported as PD and irPD due to "symptomatic deterioration." Every effort should be made to document the objective progression even after discontinuation of treatment due to symptomatic deterioration. A patient is classified as having PD and irPD due

to “symptomatic deterioration” if any of the following occur that are not either related to study treatment or other medical conditions:

- Unintentional weight loss >10% of body weight
- Decline in performance status of >1 level on ECOG scale

